- PD-L1 IHC status (IHC score of IC0/1 vs. IHC score of IC2/3)
- Prior neoadjuvant chemotherapy (yes vs. no)

[figure not shown]
Randomization must occur within 14 weeks after surgical resection of the primary tumor, and study drug administration should begin within 7 calendar days after randomization.

For patients in Arm A, atezolizumab will be administered intravenously (IV) on Day 1 of each 21-day cycle for 16 cycles (up to 1 year). In Arm B, patients will continually undergo observation starting on Day 1 of each 21-day cycle for 16 cycles (up to 1 year). Treatment/observation will be discontinued in the event of disease recurrence, unacceptable toxicity, withdrawal of consent, or study termination by the Sponsor.

To ensure the same frequency of study assessments between the treatment arms, including assessments for disease recurrence and safety, patients in Arm B will be required to undergo q3w medical contacts for assessments during the first year, which will consist of formal clinic visits alternating with clinical contacts (either via telephone call or formal outpatient clinic visit) for symptom and adverse event assessment.

Patients in the control arm will not be allowed to cross over to receive atezolizumab treatment within this study.

Figure 3 Study Schema

UC = urothelial carcinoma.

All patients will undergo scheduled assessments for tumor recurrence at baseline and every 12 weeks (approximately every 4 cycles) in the first year following randomization. Upon completion of the treatment/observation period, surveillance for tumor recurrence will be performed every 12 weeks for Years 2–3; every 24 weeks for Years 4–5; and at Year 6 (approximately 48 weeks after the last assessment in Year 5). *After the primary analysis, patients in Years 2–3 of the study may be assessed for tumor recurrence every 24 weeks.* In the absence of a DFS event (see definition in Section 3.4.1.1), surveillance for tumor recurrence should continue regardless of whether patients start new anticancer therapy, until withdrawal of consent, loss to follow-up, or study termination by the Sponsor, whichever occurs first. For patients with muscle-invasive bladder cancer

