4.5.6 Laboratory, Biomarker, and Other Biological Samples

Samples for hematology, serum chemistries, coagulation, urinalysis, and the pregnancy test will be analyzed at the study site's local laboratory. Central laboratories will coordinate the collection of archival tumor, fresh tumor, and leftover tumor tissue and blood samples for the assessment of atezolizumab pharmacokinetics and pharmacodynamic biomarkers, ATA assays, and auto-antibody testing. Instruction manuals and supply kits will be provided for all central laboratory assessments.

Local laboratory assessments will include the following:

- Hematology (CBC, including RBC count, hemoglobin, hematocrit, WBC count with differential [neutrophils, eosinophils, lymphocytes, monocytes, basophils, and other cells], and platelet count)
- Serum chemistries (glucose, BUN or urea, creatinine, sodium, potassium, magnesium, chloride, bicarbonate, calcium, phosphorus, total bilirubin, ALT, AST, alkaline phosphatase, LDH, total protein, and albumin)
- Coagulation (aPTT and INR)
- Serum pregnancy test during screening and serum or urine pregnancy tests during the study (for women of childbearing potential, including women who have had a tubal ligation)
- Urinalysis (specific gravity, pH, glucose, protein, ketones, and blood)
- Thyroid function testing (thyroid-stimulating hormone [TSH], free T3, free T4)

- All patients will be tested for HIV prior to the inclusion into the study, and HIV-positive patients will be excluded from the clinical trial.
- HBV serology (HBsAg, antibody to HBsAg [anti-HBs], anti-HBc)
 - HBV DNA is required on or before Cycle 1, Day 1 if patient has negative serology for HBsAg and positive serology for anti-HBc.
- HCV serology (anti-HCV)

Instruction manuals and supply kits will be provided for all central laboratory assessments. The following assessments will be performed at a central laboratory or by the Sponsor:

- ATA assays (patients assigned to atezolizumab only)
 - Serum samples will be assayed for the presence of ATAs to atezolizumab with use of validated immunoassays.
- PK assays (patients assigned to atezolizumab only)
 - Serum samples will be assayed for atezolizumab concentration with use of a validated immunoassay.
 - Residual PK and ATA samples will be retained for further method development, validation and characterization. Samples will be stored for 5 years after the study results have been reported.

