5.3.5.5 Abnormal Laboratory Values

Not every laboratory abnormality qualifies as an adverse event. A laboratory test result must be reported as an adverse event if it meets any of the following criteria:

- Is accompanied by clinical symptoms
- Results in a change in study treatment (e.g., dosage modification, treatment interruption, or treatment discontinuation)

- Results in a medical intervention (e.g., potassium supplementation for hypokalemia) or a change in concomitant therapy
- Is clinically significant in the investigator's judgment

Note: For oncology trials, certain abnormal values may not qualify as adverse events.

It is the investigator's responsibility to review all laboratory findings. Medical and scientific judgment should be exercised in deciding whether an isolated laboratory abnormality should be classified as an adverse event.

If a clinically significant laboratory abnormality is a sign of a disease or syndrome (e.g., alkaline phosphatase and bilirubin 5×ULN associated with cholestasis), only the diagnosis (i.e., cholestasis) should be recorded on the Adverse Event eCRF.

If a clinically significant laboratory abnormality is not a sign of a disease or syndrome, the abnormality itself should be recorded on the Adverse Event eCRF, along with a descriptor indicating if the test result is above or below the normal range (e.g., "elevated potassium," as opposed to "abnormal potassium"). If the laboratory abnormality can be characterized by a precise clinical term per standard definitions, the clinical term should be recorded as the adverse event. For example, an elevated serum potassium level of 7.0 mEq/L should be recorded as "hyperkalemia."

Observations of the same clinically significant laboratory abnormality from visit to visit should only be recorded once on the Adverse Event eCRF (see Section 5.3.5.4 for details on recording persistent adverse events).

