Appendix 1 Schedule of Assessments (cont.)

Study Procedures	Both Arms	Arm A (Atezolizumab)		Arm B (Observation)			Both Arms
	Screening for Randomization	All Cycles	Discontinuation ^a	Cycles 1, 3, 5, 7, 9, 11, 13, and 15	Cycles 2, 4, 6, 8, 10, 12, 14, and 16	Discontinuation ^a	Follow-Up
	Days -28 to -1	Day 1 (± 3 Days for Cycles ≥ 2) ^b	≤ 30 Days after Last Dose	Day 1 (± 3 Days for Cycles ≥ 2) ^b	Day 1 (± 3 Days) ^b	≤ 30 Days after Last Visit	
Urinalysis ^m	x	x ^{n,f}	x	x ⁿ		x	
TSH, free T3, free T4	x	x ^{o,f}	x				
Auto-antibody testing ^p		x	x				
Serum sample for ATA assessment		See Appendix 2					
Serum sample for PK sampling		See Appendix 2					
Blood samples for biomarkers		See Appendix 2					
Optional whole blood sample for RCR ^q		x ^q		x ^q			
Study drug infusion ^r		x					
Archival/screening FFPE tumor tissue specimen or 15 unstained slides ^s	x						
Fresh biopsy (mandatory sample ^t and optional RCR sample ^u)		At the time of radiographic confirmation of disease recurrence ^{t,u}					
Assessments for UC recurrence ^v	x	Every 12 weeks following randomization (± 7 days; at approximately every four cycles) in first 3 years; every 24 weeks (± 10 days) for Years 4 and 5; and at Year 6 (± 10 days), until death, disease recurrence, loss to follow-up, end of Year 6, or withdrawal of consent. After the primary analysis, patients in the first 3 years of the study may be assessed for tumor recurrence every 24 weeks.					
Concomitant medications ^w	x	x	x	x	x	x	

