Appendix 1 Schedule of Assessments (cont.)

- ^g Complete and limited physical examinations are defined in Section 4.5.3.
- ^h Vital signs include heart rate, respiratory rate, blood pressures, and temperature and will be performed as standard of care if clinically indicated for patients randomized to the observation arm. For patients randomized to the atezolizumab treatment arm, for the first infusions of study drug, the patient's vital signs should be determined up to 60 minutes before the start of infusion, and if clinically indicated, during and 30 (\pm 10) minutes after the infusion. For subsequent infusions, vital signs will be recorded if clinically indicated or if symptoms occurred in the prior infusion.
- ⁱ ECG recordings will be obtained during screening and when clinically indicated during study. ECGs for each patient should be obtained from the same machine wherever possible. ECG recordings must be performed after the patient has been resting in a supine position for at least 10 minutes.
- ^j See Section 4.5.6 for serology tests. HIV testing to be performed in accordance with national and/or institutional guidelines. HBV DNA must be collected on or before Cycle 1, Day 1 in patients who have negative serology for hepatitis B surface antigen and positive serology for anti HBe.
- ^k Blood samples collected to monitor safety will be collected in patients randomized to both arms. Hematology consists of CBC, including RBC count, hemoglobin, hematocrit, WBC count with automated differential (neutrophils, lymphocytes, eosinophils, monocytes, basophils, and other cells), and platelet count. A manual differential can be done if clinically indicated. Refer to Section 4.1.1 for a list of laboratory results to be obtained within 14 days prior to the first dose of study treatment.
- ^l Serum chemistry includes BUN, creatinine, sodium, potassium, magnesium, chloride, bicarbonate, calcium, phosphorus, glucose, total bilirubin, ALT, AST, alkaline phosphatase, LDH, total protein, and albumin. Refer to Section 4.1.1 for a list of laboratory results to be obtained within 14 days prior to the first dose of study treatment.
- ^m Urinalysis (specific gravity, pH, glucose, protein, ketones, and blood).
- ⁿ On Day 1 of Cycle 3 and every two cycles thereafter.
- ^o On Day 1 of Cycle 5 and every four cycles thereafter.

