Risks Associated with Atezolizumab and Guidelines for Management of Adverse Events Associated with Atezolizumab (cont.)

Table 4 Management Guidelines for Endocrine Events

Event	Management
Asymptomatic hypothyroidism	
 • Continue atezolizumab. • Initiate treatment with thyroid replacement hormone. • Monitor TSH weekly.
Symptomatic hypothyroidism	
 • Withhold atezolizumab. • Initiate treatment with thyroid replacement hormone. • Monitor TSH weekly. • Consider patient referral to endocrinologist. • Resume atezolizumab when symptoms are controlled and thyroid function is improving.
Asymptomatic hyperthyroidism	
TSH \geq 0.1 mU/L and $<$ 0.5 mU/L:
 
 • Continue atezolizumab. • Monitor TSH every 4 weeks. 
TSH $<$ 0.1 mU/L:
 
 • Follow guidelines for symptomatic hyperthyroidism.
Symptomatic hyperthyroidism	
 • Withhold atezolizumab. • Initiate treatment with anti-thyroid drug such as methimazole or carbimazole as needed. • Consider patient referral to endocrinologist. • Resume atezolizumab when symptoms are controlled and thyroid function is improving. • Permanently discontinue atezolizumab and contact Medical Monitor for life-threatening immune-mediated hyperthyroidism. ^c

MRI = magnetic resonance imaging; TSH = thyroid-stimulating hormone.

- ^a Atezolizumab may be withheld for a longer period of time (i.e., > 12 weeks after event onset) to allow for corticosteroids (if initiated) to be reduced to \leq 10 mg/day oral prednisone or equivalent. The acceptable length of the extended period of time must be agreed upon by the investigator and the Medical Monitor.
- ^b If corticosteroids have been initiated, they must be tapered over \geq 1 month to \leq 10 mg/day oral prednisone or equivalent before atezolizumab can be resumed.
- ^c Resumption of atezolizumab may be considered in patients who are deriving benefit and have fully recovered from the immune-mediated event. Patients can be re-challenged with atezolizumab only after approval has been documented by both the investigator (or an appropriate delegate) and the Medical Monitor.

Appendix 9

Risks Associated with Atezolizumab and Guidelines for Management of Adverse Events Associated with Atezolizumab (cont.)

Table 4 Management Guidelines for Endocrine Events (cont.)

Event	Management

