4.5 SAFETY ANALYSES

Unless specified otherwise, the safety analyses described below will be conducted for the safety population (see Section 4.1.2), with patients grouped according to whether any atezolizumab treatment was received (i.e., patients who received any dose of atezolizumab will be included in the atezolizumab arm).

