4.5.2 Adverse Events

Verbatim descriptions of adverse events will be mapped to Medical Dictionary for Regulatory Activities (MedDRA terms). Treatment emergent events (defined as events occurring on or after the first dose of atezolizumab, or, for patients in the observation arm, after the date of randomization) will be summarized by MedDRA term, appropriate MedDRA levels, and NCI CTCAE (National Cancer Institute, Common Terminology Criteria for Adverse Events) v4.0 grade. For each patient, multiple occurrences of the same event will be counted once at maximum severity reported will be used in the summaries. Adverse events will be summarized regardless of relationship to study drug as assessed by the investigator. All adverse events, adverse events leading to withdrawal of study drug, adverse events leading to dose interruption, Grade ≥ 3 adverse events, serious adverse events, adverse events related to study drug, adverse events of special interest, and immune-mediated adverse events will be summarized. Deaths and cause of death will be summarized.

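### After screening, thyroid function is scheduled in the atezolizumab arm only, so the by-group summaries of thyroid and immune-mediated events are biased upward on atezolizumab by an amount the documents cannot fix

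*SAP*

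**What the plan says.** Protocol Appendix 1, repeated in SAP Appendix 2, has a row for "TSH, free T3, free T4". It is marked at screening for both arms, then at Arm A cycles and Arm A discontinuation. Every Arm B column after screening is blank. The footnote sets the Arm A timing: "On Day 1 of Cycle 5 and every four cycles thereafter".

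Protocol 4.5.6 lists "Thyroid function testing (thyroid-stimulating hormone [TSH], free T3, free T4") among the local laboratory tests without limiting it to one arm, although the same section marks antibody, pharmacokinetic and auto-antibody tests as atezolizumab-only. Protocol 3.1 explains the Arm B contact schedule by the aim "To ensure the same frequency of study assessments between the treatment arms, including assessments for disease recurrence and safety".

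For asymptomatic hypothyroidism on atezolizumab, Appendix 9, Table 4 says: "Initiate treatment with thyroid replacement hormone". Protocol 5.3.5.5 says: "A laboratory test result must be reported as an adverse event if it meets any of the following criteria". A medical intervention, a change in concomitant therapy and a change in study treatment are among those criteria.

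SAP 4.5 runs the safety summaries "with patients grouped according to whether any atezolizumab treatment was received". SAP 4.5.2 lists all events, and then "adverse events of special interest, and immune-mediated adverse events will be summarized", with no limit or caveat for tests done in one arm. Hypothyroidism is a special-interest event under protocol 5.2.3, whose heading confines that category to Arm A.

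**The concern.** An adverse-event table with two columns invites the reader to take the difference as the drug's effect. That requires a similar chance of finding the event in both groups. For a condition that can be silent, detected by a blood test done on schedule in one arm and not in the other, the chances differ.

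Hypothyroidism is a listed atezolizumab risk (protocol 5.1.1), so these are rows that readers will use to judge toxicity in an adjuvant population. The SAP limits one-arm data elsewhere (exposure in 4.5.1, anti-drug antibody results in 4.7) but does nothing comparable here.

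**Working it through.** The documents state no thyroid incidence, detection rate or arm ratio, so there is no planned figure to reproduce.

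**Scheduled tests.** From Cycle 5, every four cycles, within 16 cycles: Cycles 5, 9 and 13, that is Days 85, 169 and 253 by (cycle − 1) × 21 + 1. With the discontinuation visit, an Arm A completer has up to 4 scheduled tests after screening. An Arm B patient has 0.

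**From test to adverse event.** In Arm A, asymptomatic hypothyroidism leads to hormone replacement (Appendix 9, Table 4), which meets the intervention criterion in 5.3.5.5. Asymptomatic TSH below 0.1 mU/L follows the symptomatic guideline, under which study drug is withheld; that meets the change-in-treatment criterion. Asymptomatic TSH from 0.1 to below 0.5 mU/L is only monitored, so it becomes an event only on the investigator's judgment. In Arm B a silent case enters this chain only if someone orders a test outside the schedule.

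**Ratio with no drug effect.** Let s be the share of new cases with symptoms that prompt testing in either arm, r the share of silent cases found by scheduled tests and recorded in Arm A, and u the share of silent cases found by unscheduled tests in Arm B. All three are assumptions.

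Ratio A:B = [s + (1 − s)r] / [s + (1 − s)u]

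| s | r = 1, u = 0 | r = 1, u = 0.25 | r = 0.75, u = 0.25 |
|---|---|---|---|
| 0.10 | 10.0 | 3.1 | 2.4 |
| 0.20 | 5.0 | 2.5 | 2.0 |
| 0.25 | 4.0 | 2.3 | 1.9 |
| 0.33 | 3.0 | 2.0 | 1.7 |
| 0.50 | 2.0 | 1.6 | 1.4 |
| 0.75 | 1.3 | 1.2 | 1.2 |

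When r = 1 this is 1/d, where d = s + (1 − s)u is the share of all Arm B cases that surface. So d = 50% gives 2, d = 20% gives 5 and d = 75% gives 1.3. If r and u were equal, the ratio would be 1.0.

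**Absolute size.** With background incidence b (assumed 1% to 3%) and r = 1, the spurious excess is b(1 − d). For b = 1%, d = 0.5: 0.5 percentage points. For b = 3%, d = 0.2: 2.4 points. About 800 patients at 1:1 is about 400 per arm, so this is 2 to 9.6 extra patients in Arm A.

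**How it might look.** With b = 3% and no drug effect, d = 0.25 gives an expected 12 against 3 cases, and a reader's own two-proportion test would reach p < 0.05 about 65% of the time. With d = 0.5 the expected counts are 12 against 6 and the chance is about 30%.

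**All-event total.** A thyroid event adds a patient to this total only if that patient has no other event. Protocol 1.2.2.2 reports any-event rates of 94.9% to 97.4% on atezolizumab in metastatic disease, leaving at most 5.1% without one. If similar rates held here and thyroid events were independent of other events, 9.6 × 0.051 is about 0.5 of a patient.

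**Reporting windows.** The sixteenth dose falls on about Day 316 (15 × 21 + 1). Arm A special-interest events run to about Day 406 (316 + 90) and other events to Day 346 (316 + 30). Arm B runs to about Day 395 (365 + 30). For completers these windows contribute little beside the testing difference.

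**The case against.** The strongest reply is that the size is guesswork. A reader might infer that hypothyroidism will look several times more frequent on atezolizumab even with no drug effect. The documents do not support that as fact. A ratio of 3 or more needs s of about one third or less with no incidental testing in Arm B, or about 0.10 if a quarter of silent cases are found there anyway. This objection stands as to size. It does not touch direction, as long as scheduled testing finds more silent cases than chance testing does.

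Arm B is also not unobserved. It has three-weekly contacts for symptoms and adverse events (protocol 3.1), and its events are reported (5.3.1). Symptomatic cases can surface in both arms, so dropping Arm B thyroid events from the tables would discard valid data. That stands, and the fix keeps them.

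Two further inferences fail. Not every thyroid abnormality in Arm A becomes an event, as the mild hyperthyroidism row shows. And the special-interest total is not distorted chiefly by thyroid testing: protocol 5.2.3 and 5.3.1 collect that category in Arm A only, so it is not comparable in any case. SAP 4.5.2 gives no term list by which it could be rebuilt for Arm B.

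Finally, the SAP plans no test, ratio or difference for adverse events. That limits the harm to interpretation but does not remove it: columns set side by side are read as a comparison.

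**Conclusion.** The concern holds for direction and for the missing safeguard. Scheduled thyroid testing after screening is one-sided, a treated asymptomatic case in Arm A is reportable, and SAP 4.5.2 summarises thyroid and immune-mediated events by group without qualification. The between-group contrast mixes drug effect with detection.

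Its size cannot be derived from the documents. About 1.2 to 10 fold is the spread over the tabulated assumptions, and 2 to 5 fold rests on full detection in Arm A with 20% to 50% of Arm B cases surfacing. In patients, the excess is about 2 to 10 of 400 under an assumed 1% to 3% incidence. How far the immune-mediated total moves also depends on a definition that SAP 4.5.2 does not give. Type I error for disease-free and overall survival is unaffected.

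**What to change.** In SAP 4.5.2:

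- Keep thyroid events tabulated in both groups. Add a footnote that Arm B had no scheduled thyroid tests after screening and that the difference must not be read as drug effect.
- Show the immune-mediated total with and without thyroid terms.
- Present adverse events of special interest for atezolizumab-treated patients only, citing protocol 5.2.3.

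In the protocol, reconcile 4.5.6, which lists thyroid tests with no arm restriction, with the Appendix 1 grid. If Arm B testing did take place under 4.5.6, the footnote should describe it.

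The cost is SAP wording and a few extra table rows; the SAP changes need no new data. The limit is that no unbiased between-arm estimate for thyroid events will be available: the change makes the table honest about that but cannot supply the missing tests.

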4.5.3 Laboratory Data

Laboratory data will be classified according to NCI CTCAE v4.0. Highest NCI CTCAE v4.0 grade post-baseline will be reported and shift tables from baseline to worst value during the study post-baseline will be presented. Selected laboratory tests will be summarized descriptively over time including changes from baseline.

A Hy's law analysis will be provided. The potential Hy's law quadrant is defined as alanine aminotransferase or aspartate aminotransferase increases above 3-fold the upper limit of normal (ULN) with concomitant total bilirubin increases above 2-fold the ULN.

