6.5 SAFETY ANALYSES

Safety analyses will include all patients who received at least one dose of study treatment (atezolizumab) and all patients randomized to the observation arm with at least one safety assessment. Exposure to atezolizumab treatment and length of safety follow-up will be summarized by arm.

Verbatim descriptions of adverse events will be mapped to MedDRA terms. Treatment-emergent events (defined as events occurring on or after the first dose of atezolizumab, or, for patients in the observation arm, after the date of randomization) will be summarized by MedDRA term, appropriate MedDRA levels, and NCI CTCAE v4.0 grade. For each patient, the maximum severity reported will be used in the summaries. Adverse events will be summarized regardless of relationship to study drug as assessed by the investigator. All adverse events, adverse events leading to withdrawal of study drug, adverse events leading to dose reduction or interruption, Grade ≥ 3 adverse events, serious adverse events, and adverse events of special interest will be summarized. Deaths and cause of death will be summarized.

Changes in NCI CTCAE grade for selected laboratory tests will be tabulated by arm. Changes in selected vital signs will be summarized. ATA results will be summarized and listed by patient for patients in Arm A only.

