Appendix 1 Schedule of Assessments

Study Procedures	Both Arms	Arm A (Atezolizumab)	Arm B (Observation)			Both Arms	
	Screening for Randomization	All Cycles	Discontinuation ^a	Cycles 1, 3, 5, 7, 9, 11, 13, and 15	Cycles 2, 4, 6, 8, 10, 12, 14, and 16	Discontinuation ^a	
	Days –28 to –1	Day 1 (± 3 Days for Cycles ≥ 2) ^b	≤ 30 Days after Last Dose	Day 1 (± 3 Days for Cycles ≥ 2) ^b	Day 1 (± 3 Days) ^b	≤ 30 Days after Last Visit	Follow-Up
Signed Informed Consent Form(s) ^c	x						
Review of eligibility criteria	x						
Medical, surgical, and cancer histories, including demographic information ^d	x						
Pregnancy test ^e	x	x	x				
ECOG performance status	x	x ^f	x	x ^f		x	
Age-adjusted Charlson comorbidity index (ACCI)	x						
Complete physical examination ^g	x		x			x	
Limited physical examination ^g		x ^f		x ^f			
Weight	x	x	x	x		x	
Height	x						
Vital signs ^h	x	x	x	x		x	
12-lead electrocardiogram ⁱ	x	x	x				
HIV, HCV serology ^j	x						
Hematology ^k	x	x ^f	x	x ^f		x	
Serum chemistry ^l	x	x ^f	x	x ^f		x	
Coagulation panel (aPTT, INR)	x		x			x	

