4.3 ANALYSIS OF TREATMENT GROUP COMPARABILITY

Demographic variables (age, sex, race/ethnicity), stratification factors (nodal status, number of lymph nodes resected, tumor stage, PD-L1 status, and prior neo-adjuvant chemotherapy) and baseline and disease characteristics (e.g., ACCL, time since initial

diagnosis, time since surgery, surgery-related information, type of urinary diversion, and Eastern Cooperative Oncology Group [ECOG] Performance Status) will be summarized by treatment arm for the ITT population.

Unless otherwise noted, the baseline value of any variable will be defined as the last available value prior to the first administration of study treatment for the atezolizumab arm and prior to Cycle 1 Day 1 date of observation for the observation arm. Descriptive statistics (mean, median, SD, range) will be presented for continuous variables, and frequencies and percentages will be presented for categorical variables.

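### Worst-grade and shift tables for hematology and chemistry compare 16 scheduled post-baseline draws in Arm A with 8 or 9 in Arm B, which tilts them against atezolizumab

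*SAP*

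**What the plan says.** SAP 4.5.3 plans two summaries based on each patient's worst value: "Highest NCI CTCAE v4.0 grade post-baseline will be reported and shift tables from baseline to worst value during the study post-baseline will be presented". It adds a Hy's law output that looks for raised ALT or AST "with concomitant total bilirubin increases above 2-fold the ULN". It also plans a summary by time: "Selected laboratory tests will be summarized descriptively over time including changes from baseline".

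The grouping is set elsewhere. SAP 4.5 analyzes safety "with patients grouped according to whether any atezolizumab treatment was received", and Protocol 6.5 says "Changes in NCI CTCAE grade for selected laboratory tests will be tabulated by arm".

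Protocol Appendix 1 and SAP Appendix 2 give the same laboratory schedule. Hematology and serum chemistry are marked at screening, at all cycles in Arm A, at odd cycles in Arm B, and at discontinuation in both arms. The Arm B column for "Cycles 2, 4, 6, 8, 10, 12, 14, and 16" is blank for both panels; that contact may be a telephone call.

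SAP 4.3 defines baseline as the last value before first dose in Arm A, and as the last value "prior to Cycle 1 Day 1 date of observation for the observation arm". Neither document restricts the worst-value tables to shared visits or notes the difference in draw frequency.

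**The concern.** The maximum of a series cannot fall when more observations are added. If two arms have identical laboratory behavior and one is sampled about twice as often, that arm will show more patients with a high worst grade and more shifts from normal to abnormal. Someone reading the Arm A and Arm B columns side by side could take the excess for drug toxicity. In an open-label adjuvant trial against observation, these tables are part of the laboratory safety description, so an excess built in by the schedule can mislead even though nothing is tested.

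**Working it through.** The documents state no number of draws, so there is no planned figure to reproduce. The count below comes from the schedule.

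**Draws for a patient completing 16 cycles**

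- Arm A: the Cycle 1 draw precedes the infusion (Appendix 1, note below the table), so it is baseline. Cycles 2-16 give 15, plus 1 at discontinuation = 16.
- Arm B: Cycles 3, 5, 7, 9, 11, 13 and 15 give 7, plus 1 at discontinuation = 8.
- Arm B, literal reading of SAP 4.3: a Cycle 1 draw taken on the Day 1 date is not before that date, so it counts as post-baseline and gives 9. Taken up to 96 hours earlier, as Appendix 1 note f allows, it is baseline and the count stays at 8.

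**Other panels.** Urinalysis falls on the same cycles in both arms. Coagulation is tested at screening and discontinuation in both. Neither is affected. Thyroid tests have no scheduled Arm B draw after screening, so they support no between-arm worst-grade comparison.

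**Size with no drug effect.** The per-draw abnormality rate p and the within-patient correlation rho are assumptions. For independent draws, P(any abnormal) = 1 - (1 - p)^n. At p = 1% this is 1 - 0.99^16 = 14.9% against 1 - 0.99^8 = 7.7%, a ratio of 1.92. That is an upper reference, because values within a patient are correlated.

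With an exchangeable normal model and z the upper-p normal quantile:

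P(any abnormal in n draws) = integral of phi(u)[1 - c(u)^n] du, where c(u) = Phi((z - sqrt(rho) u)/sqrt(1 - rho)).

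| p | rho | Arm A, 16 | Arm B, 8 | Arm B, 9 | Ratio 16:8 | Ratio 16:9 |
|---|---|---|---|---|---|---|
| 1% | 0.3 | 11.7% | 6.8% | 7.5% | 1.73 | 1.57 |
| 1% | 0.5 | 9.1% | 5.7% | 6.2% | 1.60 | 1.47 |
| 1% | 0.8 | 4.9% | 3.6% | 3.8% | 1.37 | 1.30 |
| 5% | 0.5 | 30.9% | 21.9% | 23.3% | 1.41 | 1.32 |

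Over p of 1, 2, 5 and 10% and rho of 0.3, 0.5, 0.7 and 0.85, the ratio is 1.19-1.73 for 16 against 8 and 1.15-1.57 for 16 against 9. The absolute excess can be small: at p = 1% it runs from 11.7 - 6.8 = 4.9 points (rho 0.3) to 4.9 - 3.8 = 1.1 points (rho 0.8).

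For a shift from a normal baseline, P = integral of phi(u) c(u)[1 - c(u)^n] du / (1 - p). The ratios are 1.30-1.75 (16 against 8) and 1.24-1.58 (16 against 9).

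**What changes the ratio**

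- Persistent abnormalities: at rho = 0.999 and p = 5% it is 1.02.
- Equal early stopping: if both arms stop exponentially at the planned 20-month control median DFS, mean draws are 13.5 against 6.8 or 7.8, and the ratio is 1.19-1.73 or 1.14-1.53. Stopping or dose holds for toxicity in Arm A alone are not modeled and would lower it.
- Surveillance laboratory values: Protocol 3.1 lists laboratory evaluation within MIBC surveillance, Protocol 4.5.5 makes it as clinically indicated, and Appendix 1 marks no follow-up hematology or chemistry. If such values entered the tables at, say, 8 extra draws per arm, the counts would be 16 + 8 = 24 against 8 + 8 = 16, and the ratio 1.09-1.34.

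**The case against.** The strongest reply is that no conclusion changes. The tables are descriptive, no between-arm laboratory test is planned, the direction is against the experimental drug, and showing every observed worst value is a sound safety presentation. All of that stands. It fixes the severity at minor and is why the all-visit tables should stay.

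A reader might infer that drug effect and sampling frequency cannot be told apart at all. The documents do not support that. SAP 4.5.3 also plans summaries over time, which allow comparison at shared visits, and the unequal schedule is printed in the SAP's own appendix. Those summaries cover selected tests only, however, and do not correct the worst-grade or shift tables.

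A reader might also infer that Arm A can have 15 draws by letting the last cycle visit double as the discontinuation visit. For full completers this is weakly supported: Protocol 4.5.13.3 asks them to return after the last treatment, and Appendix 1 note a places the visit after the one-year period. The count used here is 16.

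Hy's law draws on the same chemistry panel, so the direction carries over. The assumed rates describe a single abnormality, not concurrent transaminase and bilirubin elevations, so no size can be given. Such cases must also be reported as adverse events under Protocol 5.3.5.7. More generally, adverse event tables cover only part of the gap, because Protocol 5.3.5.5 says that some laboratory abnormalities do not qualify as adverse events.

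**Conclusion.** The point holds for hematology and serum chemistry. The scheduled counts of 16 against 8 or 9 follow directly from the documents, and so does the direction: more abnormal worst values are expected in Arm A with no drug effect. The size does not follow from the documents. The ratio of about 1.15-1.73 rests on 1-10% abnormal per draw, correlation of 0.3-0.85 and completion of 16 cycles. It is smaller with persistent abnormalities, early stopping in Arm A, or equal surveillance values in the tables. It should not be read as a threat to any efficacy result, test or decision rule, or as applying to every laboratory panel. Severity is minor.

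**What to change.** In SAP 4.5.3:

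- Keep the all-visit worst-grade, shift and Hy's law outputs.
- Add supplementary hematology and serum chemistry worst-grade and shift tables restricted to draws scheduled in both arms: odd cycles after Cycle 1, plus discontinuation. For these tables, treat the Cycle 1 draw as baseline in both arms. Scheduled draws for a completer are then 7 + 1 = 8 in each arm, with an expected ratio of 1.0 under no effect.
- Footnote the difference in draw frequency on the all-visit hematology and chemistry tables and on the Hy's law output.
- Footnote that Arm B has no scheduled thyroid draw after screening.

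The cost is SAP wording, one visit filter, footnotes and a few extra tables, with no change to conduct or data collection. The added tables omit even-cycle and unscheduled values, including transient Arm A toxicity, so they must be read beside the all-visit tables and not in place of them. Their Arm B baseline departs from the literal wording of SAP 4.3 and should be labeled as such. They equalize draws only for patients who stay equally long.
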